**STUDY SUMMARY**

Study Title:	DEVELOPMENT OF A NEW APPROACH TO MEASURE THE VOLUME OF BREAST TISSUE REMOVED DURING WIDE LOCAL EXCISION USING SPECIMEN WEIGHT AND MAMMOGRAPHIC DENSITY
Local Study Reference:	UHDB/2019/088
Study Design:	Single-centre proof-of concept study
Study Participants:	Women undergoing breast conserving surgery for breast cancer as standard care.
Planner Number of Sites:	1
Planned Sample Size:	Phase 1: 110; Phase 2: 246
Treatment Duration:	n/a
Follow Up Duration:	n/a
Planned Start Date:	01/09/2023
Planned Recruitment End Date:	31/10/2024
Planned Study End Date:	30/11/2024
Research Question/ Aims:	The objective of this research project is to evaluate a novel method of obtaining simple and accurate estimates of the volume of breast tissue excised during breast conserving surgery by putting the weight of the surgical specimen in relation with its radiological density. The primary endpoint is to establish whether the method is superior to the currently used method.

**FUNDING AND SUPPORT IN KIND**

Funder(s)	Financial and Non-Financial Support Given
Derby and Burton Hospitals Charity	Financial
Consultant Radiologist	Radiologists participating in the study will undertake research activities at no cost to the study.
[name]	The PI will undertake research activities at no cost to the study.

## ROLES & RESPONSIBILITIES

### **Sponsor**

The Sponsor, University Hospitals of Derby and Burton NHS Foundation Trust, take on overall responsibility for appropriate arrangements being in place to set up, run and report the research project. The sponsor is not providing funds for this study, but has taken on responsibility for ensuring finances are in place to support the research.

### **Funder**

The study is funded by Derby and Burton Hospitals Charity.

### **Study Management Committees**

#### Trial Management Group (TMG)

The trial management group will meet regularly to oversee the day-to-day management of the trial, including all aspects of the conduct of the trial. Any problems with study conduct and participating centers will be raised and addressed during TMG meetings.

#### Trial Steering Committee (TSC) and Data Monitoring and Ethics Committee (DMEC)

This is a small proof of concept study and therefore will not require a TSC or DMEC

### **Protocol Contributors**

A number of protocol contributors have been involved in the development of this protocol, these include; the Chief Investigator, Co-Investigators (incl. Statistician) and the Trial Management team. Protocol contributors are responsible for inputting into the design of the study, ensuring that it is designed transparently and efficiently.

## LIST OF ABBREVIATIONS

[figure not shown]
AE	Adverse Event
BCS	Breast Conserving Surgery
BMI	Body Mass Index
CI	Chief Investigator
CRF	Case Report Form
CT	Computed Tomography
CWPF	Chest Wall Perforator Flap
DMEC	Data Monitoring and Ethics Committee
GCP	Good Clinical Practice
GMP	Good Manufacturing Practice
ICF	Informed Consent Form
ICH	International Conference on Harmonisation of technical requirements for registration of pharmaceuticals for human use.
ISF	Investigator Site File
ISRCTN	International Standard Randomised Controlled Trials
MDT	Multi-Disciplinary Team
NHS R&D	National Health Service Research & Development
PI	Principal Investigator
PIC	Participant Identification Centre
PIS	Participant Information Sheet
QA	Quality Assurance
QC	Quality Control
RCT	Randomised Control Trial
REC	Research Ethics Committee
RT	Radiotherapy
SAE	Serious Adverse Event
SDV	Source Data Verification
SOP	Standard Operating Procedure
TMG	Trial Management Group
TSC	Trial Steering Committee
TMF	Trial Master File
VAS	Visual Analogue Scale
WLE	Wide Local Excision

STUDY FLOW CHART

[figure not shown]
Phase 1:

Phase 2:

Estimated timescale:

## STUDY PROTOCOL

### 1. BACKGROUND

There are several published methods to estimate the breast volume using mammogram measurements as reference [1,2]. All these methods are based on the assumption that breasts are equally composed of fibro-glandular tissue, which has been attributed the same density of water (1g/ml), and fatty tissue (with a density of 0.92g/ml). The resulting breast density based on this assumption is 0.958g/ml.

A similar approach has been used in attempt to estimate a wide local excision (WLE) specimen volume from its weight [3,4]. All these methods are limited by the fact that the percentage of breast fibro-glandular tissue is not the same for every woman and every surgical specimen. It does also not take into account the proportion of the specimen occupied by the breast tumour itself, which will be denser.

Breast cancer patients treated with WLE subsequently receive adjuvant breast radiotherapy (RT) to reduce the risks of local recurrence. This can be accompanied by a further radiation dose to the breast tissue adjacent to the surgical excision (tumour bed boost), which is the area at higher risk for recurrence. During surgery, metal clips are left in the breast to help the radiation oncologist to identify the target area for the boost.

The delivery of tumour bed boost in an accurate way is of paramount importance. The recently published up to 20-year follow-up data of the European Organization for Research and Treatment of Cancer (EORTC) “boost no boost” trial show that the ipsilateral recurrence rate is lower in patients receiving boost (12%) vs. no boost (16.4%) [5]. However, boost RT may result in varying degrees of focal retraction or indentation and asymmetry due to either local fibrosis or major fat necrosis resulting in breast volume loss or change of shape [6].

### 2. RATIONALE

The aim of this study is to evaluate a novel method of obtaining simple and accurate estimates of the volume of a WLE specimen by putting the specimen weight in relation with its radiological density.

In women with smaller breasts and larger tumours oncoplastic breast surgery techniques such as volume replacement with chest wall perforator flaps (CWPF) can be used to enable breast conservation and avoid deformity. In CWPF, the surgical cavity resulting from WLE is filled volume-for-volume with non-breast tissue (skin and fat) harvested from the surrounding chest wall.

A previous research study demonstrated how, in the context of CWPF volume replacement, the standard approach for tumour bed contouring (based solely on the metal clips placed by the surgeon) is not accurate (contoured volume significantly smaller than specimen volume). A new method of contouring has been proposed including the clips and the typical appearance of the flap in the planning CT scan [7,8].

On average, the tumour bed volume obtained with this method closely matched the estimated surgical specimen volume obtained from its weight (only 1.02 ml smaller on average). However, the variability between the individual cases was high (SD 43.6). This is thought to be related with the difference in breast density between the patients leading to a non-accurate estimate of the specimen volume based on its weight [8].

In the context of volume replacement surgery, having an accurate estimate of the volume of breast tissue removed with surgery could help to increase the accuracy of tumour bed contouring. If the boost volume is underestimated, then the target penumbral breast tissue will be missed (only the central portion of non-breast flap tissue would be irradiated) potentially leading to higher rates of local recurrence. If the boost volume is overestimated, then an excess dose of radiation would be administered with negative impact on the final cosmetic outcome (increased fibrosis and loss of volume).

During a meeting with a group of breast cancer patients held during the design phase of this study, the importance of accurate radiotherapy planning has been unanimously acknowledged by all participants. In fact, both under- and overestimation of the boost target volume (and subsequent increased risk of local recurrence or impaired cosmetic outcome respectively) could have negative impact on patients' quality of life and require further treatment including surgery.

To determine the long-term effects of an increased accuracy of the RT boost (impact on local recurrence rate and cosmetic sequelae) is beyond the scope of this initial project due to the timelines of these events. Nevertheless, these aspects could be potentially explored with a long-term study and the findings of the proposed research project will be of key importance in the design of that.

### 3. OBJECTIVES AND OUTCOME MEASURES/ ENDPOINTS

#### 3.1. Objectives

**Phase 1:** To develop a regression model to estimate tissue sample volume using a combination of explanatory variables potentially including specimen weight, radiological density, patient's age, patient's BMI, tumour histology and grade.

**Phase 2:** To compare the estimates of volume derived from the regression model identified in phase 1 and then the currently used estimation method (dividing the sample weight by the approximate density of 0.958g/ml to determine which method produces the most accurate estimates.

#### 3.2. Outcomes

**Phase 1 primary outcome:** A regression model using a combination of variables from specimen weight, radiological density, patient's age, patient's BMI, tumour histology and grade that predicts surgical specimen volume as accurately as possible.

**Phase 1 secondary outcomes:** not applicable.

**Phase 2 primary outcome:** The 95% limits of agreement (Bland and Altman [15]) with 95% confidence limits of the novel method using the regression model and the current method (dividing the specimen weights by 0.958, regardless of their radiological density) against the gold standard measurement of specimen volume (the water displacement / Archimedes method).

**Phase 2 secondary outcome 1:** The Intraclass correlation (ICC) of the estimates using the new method and the current method. This will indicate how strongly the two methods resemble each other.

**Phase 2 secondary outcome 2:** A within-patient comparison of the new method and the current method using a paired t-test.

#### 4. **STUDY DESIGN**

This is a proof-of-concept diagnostic study which evaluates a novel method of obtaining an estimate of the breast volume excised with a WLE by correlating specimen weight and radiological density adjusted for other variables such as age (affecting overall breast radiological density), tumour histology and grade (affecting specimen density as high-grade tumours are denser), and patient's BMI. The latter was selected as a surrogate of breast size as it is routinely measured in patients undergoing surgical procedures. It has been demonstrated that WLE surgical specimens in larger breasts are inherently larger due to the increased antero-posterior dimension of the cylindrical excision [9].

This method is then compared, together with the currently used approximate density of 0.958g/ml applied to all samples regardless of their radiological density, against volume measurement by water displacement (gold standard).

Method:

Specimen x-ray density will be assessed by a Radiologist using a Visual Analogue Scale (0-100). The presence of a tumour mass and its diameter, as well as the percentage of specimen occupied by the tumour will also be assessed. A standard procedure on how to assess specimen density with VAS and how to measure the tumour mass will be devised and training will be provided to the radiologists performing the measurements to reduce inter-observer variability.

Assessing mammographic density using a visual analogue scale (VAS) is a widely used and validated procedure and mammographic density using this methodology has been shown to correlate with a number of important factors breast cancer risk [10-12] and increased risk of interval cancers in screened populations [13]. In cancer patients it is assessed in the contra-lateral breast as the cancer itself affects breast density.

What is novel about this study is that we are assessing the density of a lumpectomy specimen using a VAS to help estimate excised volume of tissue. The density of the excised tissue may differ significantly from the overall breast density for two reasons:

- Invasive cancers contain little fat and so are a dense combination of tumour cells and fibrotic tissue even when the cancer occurs in a breast made up almost entirely of fat. The percentage of excised tissue which is cancer varies from 2% to 30%.
- Dense breast tissue is not uniformly spread throughout the breast. So, in a breast which is 50% dense tissue and 50% fat the tissue surrounding the cancer may be 100% fat or 100% dense tissue depending on the tumour location.

Following the x-ray assessment, breast specimen density will then be calculated:

Breast Specimen Density = Specimen weight / Specimen Volume.

The breast specimen volume will be modelled using regression analysis, with specimen x-ray density and other variables as explanatory variables. This will enable breast volumes to be estimated that are tailored to each specimen.

This study will require 2 phases:

**Phase 1:** obtain the equation to predict surgical specimen volumes.

**Phase 2 (proof of concept):** compare the novel method and the current method (standard density of 0.958g/ml applied to all samples regardless of their radiological density) with the gold standard (water displacement) using Limits of agreement (Bland and Altman [15]).

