## 10. STATISTICS AND DATA ANALYSIS

### 10.1. Sample Size Calculation

Phase 1: Regression model.

A detailed search of the literature found no data upon which a sample size calculation could be based. However, "rules of thumb" have been established for regression models for which sample size calculations cannot be calculated. The accuracy of several of these estimations has been assessed by Green [14] and, based on his research the following estimate method was selected:

$$S = 104 + i$$

Where S = Sample size; I = Number of independent variables (i.e. the number of variables we will use to predict the tissue volume). This is assuming the treatment effect would be moderate. Taking into account the number of variables this results in a sample size of 110.

Phase 2: Comparison of accuracy using limits of agreement analysis.

The sample size of 246 samples was calculated based on the precision of 95% confidence limits for 95% limits of agreement using the formulae taken from Bland and Altman [15]. The precision for the limits of agreement confidence interval was set at 5% as a difference of more than 5% could affect the accuracy of the boost radiotherapy in the CI's clinical judgement. The standard deviation of the differences using the current method was estimated at 23.26%, based on a clinical audit carried out by the CI between January and December 2022.

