#### **10.3.2. Outcome Analysis**

Study phase 1 primary outcome: A regression model to estimate the tissue volumes.

This phase will include the 6 explanatory / independent variables:

1. The diameter of the mass (mm)
2. The healthy tissue density (using a Visual Analogue Scale (VAS))
3. The area occupied by the tumour (% of tissue sample)
4. Specimen weight (g)
5. Patient age
6. Patient BMI

The outcome / dependent variable will be the tissue volume, measured using the water displacement / Archimedes principle.

The regression model will be fitted using a bi-directional stepwise regression. Variables will be included if they make an important improvement in the model's fit. They will be excluded if, after other variables have been included in the model, they no longer make an important improvement in the model's fit. The model will stop fitting variables when both of the following conditions are met:

1. None of the variables that are not already included will make an important difference to the model's fit if they are included.
2. All of the variables that are included do make an important difference, so none of them should be removed.

The definition of "important" improvements in the model's fit and how they will be assessed will be described in detail in the Statistical Analysis Plan.

Study phase 2: Assessing the accuracy of the model obtained from phase 1.

This phase of the study will use a second collection of tissue samples, that have not been used to develop the model. It is needed because the regression model has been developed to predict the tissue volumes of the first sample as accurately as possible. It may not estimate other patients' volumes as accurately as these patients and we need to demonstrate that, even if the estimates for

other patients are less accurate than for the original sample of patients, they are still more accurate than the current method.

Study phase 2 primary outcome: Comparison of the new regression-based method and the current method with the gold standard measurement (using the Archimedes/water-based method). The estimates will be compared to the measured tissue volumes using two limits of agreement analyses (Bland and Altman [15]).

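### Phase 1, as plainly read, enters weight and x-ray density as separate terms for volume, although density should multiply weight; modelling volume per gram would be better

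*Protocol*

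**What the plan says.** Protocol section 4 gives the physical relation, "Breast Specimen Density = Specimen weight / Specimen Volume", and says of the model: "The breast specimen volume will be modelled using regression analysis, with specimen x-ray density and other variables as explanatory variables".

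Section 10.3.2 fixes the outcome: "The outcome / dependent variable will be the tissue volume, measured using the water displacement / Archimedes principle". For the predictors it says "This phase will include the 6 explanatory / independent variables" and lists them singly: mass diameter, healthy-tissue density on a VAS, percentage of the sample occupied by tumour, specimen weight in grams, age and BMI. On fitting it says "The regression model will be fitted using a bi-directional stepwise regression". No product, ratio or logged term is mentioned. The only thing this section hands to the SAP is what counts as an important improvement in fit and how that is assessed.

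Section 10.1 sizes Phase 1 on those six variables. It sizes Phase 2 on a percentage scale: "The standard deviation of the differences using the current method was estimated at 23.26" per cent, with a precision of 5%. Neither section 3.2 nor section 10.3.2 says whether the Phase 2 limits of agreement are in ml or per cent.

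**The concern.** If density is weight divided by volume, then volume is weight divided by density, and a change in density changes volume in proportion to weight. The current method already scales with weight, because it multiplies every weight by 1/0.958. A model with separate weight and VAS terms cannot scale its density correction in this way: one VAS point moves the estimate by the same amount in a 20 g and a 150 g specimen. Least squares on untransformed volume is also driven by the heavy specimens, whereas the Phase 2 precision is set in per cent.

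The study looks for a gain from density that can only be a few per cent. A form that wastes part of that signal makes the new method look poorer than the data allow, mostly in light specimens. Under section 10.2 the Phase 1 analysis runs while Phase 2 is recruiting, so a later change of form would look post hoc.

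**Working it through.** **Inputs.** From the protocol: fat 0.92 g/ml, fibro-glandular tissue 1.00 g/ml and the comparator 0.958 g/ml (section 1); six predictors, SD 23.26% and precision 5% (section 10.1). Assumed, because the protocol does not give them: log-normal specimen weight with median 50 g and log-SD 0.3 to 0.8; VAS uniform on 0 to 100; density rising linearly with VAS from 0.92 to 1.00; VAS treated as whole-specimen density.

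**The plan's own figures.** Phase 1: 104 + 6 = 110, as stated. Phase 2: the half-width of the interval for a limit of agreement is 1.96 × s × √(c/n). With s = 23.26 and half-width 5, c = 3 gives n = 249.4 and c = 1 + 1.96²/2 = 2.92 gives n = 242.8. The stated 246 lies between them, so Phase 2 was sized in per cent.

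**Correct size of the density effect.** Going from VAS 0 to 100 should lower volume by W × (1/0.92 − 1/1.00) = 0.087 × W:
- 20 g: 1.7 ml
- 50 g: 4.3 ml
- 150 g: 13.0 ml

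**What an additive fit does.** Its VAS effect is close to 0.087 times the mean weight. At log-SD 0.6 the mean is 50 × exp(0.18) = 59.9 g, so the effect is about 5.2 ml for every specimen. That is three times too large at 20 g and less than half the right size at 150 g.

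**Where it loses to 0.958.** Relative to the correct effect, the additive model is wrong by an amount proportional to |mean − W|, while the 0.958 method, which makes no density correction, is wrong by an amount proportional to W. The additive model is therefore worse below about half the mean weight. The share of specimens below that point is Φ((s²/2 − ln 2)/s), where s is the log-SD.

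**Worked example** (log-SD 0.7). The fit is V = 2.79 + 1.042 W − 5.56 x, with x = VAS/100.
- 20 g, all fat: true 20/0.92 = 21.74 ml; additive 2.79 + 20.84 = 23.63 ml (+8.7%); 0.958 method 20.88 ml (−4.0%).
- 100 g, all fat: true 108.70 ml; additive 107.00 ml (−1.6%); 0.958 method 104.38 ml (−4.0%).

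**Over the assumed spread, without measurement noise:**

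| log-SD of weight | Share below half the mean | % error SD, additive | % error SD, 0.958 | SD of differences in ml, additive v 0.958 |
|---|---|---|---|---|
| 0.3 | 1.5% | 0.8% | 2.4% | 0.4 v 1.4 |
| 0.6 | 20% | 2.5% | 2.4% | 1.0 v 1.8 |
| 0.8 | 32% | 4.8% | 2.4% | 1.6 v 2.4 |

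In the lightest quarter of specimens the root-mean-square error is 1.5% (additive) against 2.4% (0.958) at log-SD 0.3, and about 4.7% against 2.4% at log-SD 0.6. A multiplicative form has an error of about 0.05% throughout.

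**At the planned size** (110 to develop, 246 to validate, log-SD 0.6, weight and VAS only), the share of simulated studies in which each form had a larger percentage SD than 0.958 was:
- 5% measurement noise: additive about 63%, volume/weight form under 1%.
- 10% noise: about 77% and 14%.
- 20% noise: about 93% and 74%.

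At every spread and noise level tried, the volume/weight form had a lower average SD than the additive form, in per cent and in ml.

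**The case against.** The form is inferred. Section 10.3.2 writes no equation, gives no unit for volume and does not exclude a log scale or a product term. A log-log model on the same six variables would fit its words, keep 110 patients and remove the problem, and the SAP is not at hand. This stands as a caution. But the outcome and the predictors are stated in the protocol, and only the criterion for important improvement is deferred, so the additive reading is the plain one.

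The comparison with 0.958 also turns on an unknown. At log-SD 0.3 the additive model wins, even in the lightest quarter. Noise-free and pooled in ml, it wins at every spread in the table, although that advantage can vanish with noise: at log-SD 0.7 and 10% noise the SDs are 8.82 ml against 8.66 ml. This stands too.

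A reader might infer that the new method would fail in Phase 2 because of its algebra, and that a multiplicative form would rescue it. The documents do not support that. On the protocol's densities, the 0.958 method errs by only 0.92/0.958 − 1 = −4.0% to 1.00/0.958 − 1 = +4.4%, against a stated SD of 23.26%. Most of that SD must have another source, which no functional form removes. If it is all treated as measurement noise (assumption), at log-SD 0.6 the percentage SD is about 26% for the additive form and about 24% for 0.958, and the multiplicative form does no better than 0.958.

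Finally, the protocol's VAS scores healthy tissue, with tumour size and tumour percentage as separate candidates. The full six-variable stepwise model was not simulated.

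**Conclusion.** The point holds as a recommended improvement. On its plain reading, section 10.3.2 adopts a form that does not match the relation in section 4: it over-corrects specimens lighter than the mean and under-corrects heavier ones. That mismatch is certain for any additive model of untransformed volume.

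Its cost relative to 0.958 is conditional. Noise-free, it runs from a clear win for the additive model (0.8% against 2.4% at log-SD 0.3) to a clear loss (4.8% against 2.4% at log-SD 0.8), with break-even just below 0.6. These figures rest on the assumed weight distribution, uniform VAS and linear link from VAS to density. The protocol therefore does not show that the additive model must do worse than current practice, or that the planned comparison is invalid, and the point should not be graded as a mandatory correction. What favours the change is that the volume/weight form beat the additive form in every setting tried and needs no further data.

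**What to change.** In sections 4 and 10.3.2, make the Phase 1 outcome volume/weight, or log(volume/weight), regressed on VAS density, tumour percentage and the other candidates. Obtain predicted volume by multiplying the (back-transformed) prediction by weight.

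Do not present a no-intercept fit of volume on weight and weight × VAS as equivalent. It has the right shape, but it is still a least-squares fit of volume and so is still dominated by heavy specimens.

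In sections 3.2 and 10.3.2, state that the Phase 2 limits of agreement use percentage differences, the scale on which section 10.1 sized Phase 2. Limits in ml can be reported alongside.

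The cost is wording in the protocol and SAP, settled before Phase 1 is fitted. The variables, data and Phase 2 size do not change. With the same six candidates Phase 1 stays at 110; adding a product term instead would give 104 + 7 = 111.
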